# 1 Preliminary Remarks

The statistical analyses plan was written in its first version in November/Dezember 2015 and was then finalized in March 2016. The follow-up data was analyzed beginning April 2016 until October 2016. Thus, the analysis plan was written before analyzing the follow-up data. However, the baseline data was analyzed since 2013 and the design paper was published in 2011. At the time of the publication of the design paper, the study statistician ([name]) was not yet employed in the DZNE and was therefore neither involved in designing the DelpHi-MV trial, nor in writing the design paper. The statistical analyses plan therefore is not coherent with the design paper in several points. The statistical analyses plan here only describes the efficacy analyses regarding the primary endpoints of the DelpHi trial.

The DelpHi cohort consists of individuals (above 70 years) who were screened positively on dementia. The sampling was done in primary care in the general practice (GP). Additionally, if possible, the principle care giver was included into the study. The GP was randomized by fair coin tossing to care as usual or intervention group. Thus, DelpHi is a cluster randomized clinical trial and all analyses have to respect the stochastic dependency of the data on the GP clustering. The randomization was done before baseline assessment of the individuals and the intervention cannot be classified as blinded, neither on the level of the GP, nor on the level of the study participant. The DelpHi trial can be classified as exploratory as no effect sizes a priori were known for the complex intervention that was performed. Moreover, the trial is clearly a pragmatic trial as it is implemented in primary care. Thus, the internal validity is potentially limited and several sources of bias (especially selection, attrition and performance bias) bias have to be assessed.

The power calculations mentioned in the design paper did not reflect the clustering of the data. The power of cluster randomized trials is not only a function of effect size, significance level and sample size, but dependent on the parameters of the concrete parameters of the clustering which were not known before sampling the data. In general, the power of a cluster randomized trial is lower in comparison to a randomized trial of equal sample size. The concrete loss of power is a function of the

intra-class correlation (ICC) of the outcome, the number and size of the clusters and the variability of the cluster sizes in the sample. It is known that with higher ICC the statistical power gets lower. If the ICC would be zero, normal power calculations apply. Thus, the sample size calculations noted in the design paper can be seen as upper bounds assuming that the ICC is zero for all outcome parameters. More accurate power calculations were therefore performed during the baseline sampling when first estimates of the ICCs where known and can be found at the end of this document.

## 2 Analysis Plan

### 2.1 Definition of the Primary Efficacy Endpoints

The design paper defined four dimensions of primary endpoints:

- (1) Quality of life
- (2) Caregiver burden
- (3) Behavioural and psychological symptoms of dementia
- (4) Pharmacotherapy with an antidementia drugs and prevention or suspension of potentially inadequate medication (PIM)

The fourth dimension includes two outcome measurements (antidementia drug treatment) and the suspension of PIM, thus, in total five outcome variables are derived. The first follow-up values on these dimensions (12 months after baseline) were defined as efficacy endpoints.

### 2.2 Operationalization of the Primary Endpoints

#### (1) Quality of life

Quality of life was measured using the Quality of Life in Alzheimer's Disease instrument [1]. It consists of 13 Lickert scale items that covers the following dimensions: physical health, energy level, mood, living situation, relationship with family members, caregivers and friends, memory as well as the ability to meaningful activities and financial situations. This instrument has been shown reliable and valid ratings by persons with mild to moderate dementia. Higher scores indicated better quality of life. The mean response on all answered items is used as outcome measurement, regardless whether the response on single items is missing. The mean response is treated as an interval scaled metric outcome.

## **(2) Caregiver burden**

Caregiver burden was measured via the Berliner Inventar zur Angehörigenbelastung (BIZA-D) [2]. The BIZA-D was developed to assess objective and subjective burden due to caring for a PWD. It consists of 88 items covering 20 dimensions of caregiver burden. Objective burden is divided into six dimensions, assessed by 25 items: 1) basic care tasks, such as supporting eating and hygiene (seven items), 2) extended care tasks, such as supporting grocery shopping and legal affairs (three items), 3) motivation and guidance (four items), 4) emotional support (four items), 5) support of the maintenance of social contacts (3 items) and 6) supervision (four items). Each item has to be rated regarding the frequency of the support needed on a 5-point scale (e.g., supervision: Does the patient need this type of support 1=always, 2=mostly, 3=partly, 4=hardly, 5=not at all). Subjective burden is divided into a) the subjective burden of behavior change (six dimensions: burden due to cognition with four items, aggression with five items, depression with four items, disorientation with five items, late symptoms with three items, and loss of relationship with five items); b) the subjective burden of perceived conflicts between needs and responsibilities to care (six dimensions: burden due to personal constraints with nine items, negative evaluation of one's own caring with four items, missing social appreciation with four items, financial losses with four items, personal development with three items, missing institutional support with three items); and c) role conflicts (two dimensions; professional role conflicts with four items, family role conflicts with five items).

From analyzing the baseline data, it was known that the 20 sum scores of the scales were highly intercorrelated with each other. Consequently, in a principle component analysis, one principle component explaining 38.6% of variance dominated. As the sequential analyses of each scale would lead to massive multiple testing, the first principle component of the BIZA-D is chosen as outcome parameter, representing a compound measure of the caregiver burden. This compound measurement is treated as an interval scaled metric outcome.

## **(3) Behavioral and psychological symptoms of dementia**

The behavioral and psychological symptoms of dementia were operationalized by the Neuropsychiatric Inventory (NPI), developed by the Alzheimer's Disease Cooperative Study investigators [3]. The NPI represents an interview by proxy on twelve dimensions of neuropsychiatric behaviors, i.e. delusions, hallucinations, agitation, dysphoria, anxiety, apathy, irritability, euphoria, disinhibition, aberrant motor behavior, night-time behavior disturbances, and appetite and eating abnormalities. The severity and frequency of each neuropsychiatric symptom are rated on the basis of scripted questions administered to the patient's caregiver. A total NPI score is calculated as the product sum of the frequency by severity scores within each domain. The NPI also assesses the amount of caregiver distress engendered by each of the neuropsychiatric disorders, but the caregiver distress scores were not used in our analysis. The total score of all twelve scales were used as interval scale metric outcome variable as supposed in the NPI manual.

#### **(4) Pharmacotherapy with an antidementia drugs**

Antidementia drug treatment was defined as in Wucherer et al. [4] The computer-based collection of primary data on medication in the context of the home medication review includes both prescription drugs (Rx) and over-the-counter (OTC) drugs. The assignment was integrated using a master file of the Pharmaceutical Index (GKV-Arzneimittelindex) [5]. Active substances were coded according to the Anatomical Therapeutic Chemical (ATC) classification system (German Modification)[6]. The outcome variable is dichotomous with individuals taking one of the following drugs (N06DA02: donepezil; N06DA03: rivastigmine; N06DA04: galantamine; N06DA52: donepezil and memantine; N06DX01: memantine) coded with “1”. Individuals not taking one these drugs were coded with “0”.

#### **(5) Prevention or suspension of potentially inadequate medication (PIM)**

Suspension of PIM taking was defined according to Priscus list [7]. A list of all ATC codes considered as PIMs is given in the appendix. From the baseline analyses, it was known that multiple prescriptions of PIMs are seldom in the study population (Wucherer et al. 2016). Thus, for efficacy analyses, we dichotomize the PIM prescriptions: “1”= one or more PIMs prescribed; “0”= no PIM prescribed.

## **2.3 Efficacy Analyses**

### **2.3.1 Per protocol analyses**

#### **2.3.1.1 Definition of the analyses set**

We define the per protocol analysis as complete case analyses. The only reason not to be included into the per-protocol analysis is due to missing data in the baseline assessment or the follow-up assessment. Contaminations by changing treatment assignments after randomization are impossible due to the study design. The main reason for missing data is supposed to be drop-out because of death or withdrawal of informed consent.

#### **2.3.1.2 Primary efficacy Analyses**

For primary efficacy analyses, for each of the main outcome of the study a separate generalized linear mixed model is fitted with the model specification corresponding to the scale level of the outcome under investigation. Thus, for quality of life, caregiver burden and neuropsychiatric symptoms linear mixed regressions will be used assuming a Gaussian distribution, while for antidementive drug treatment and PIM prescription logistic mixed models will be used. To account for the stochastic dependency of patients treated by the same GP, the GP will be included as random effect variable.

The follow up outcome variable at  $T_1$  (twelve months after finishing the baseline) will be the dependent variable in these analyses; the study group is the predictor of interest, while the baseline value ( $T_0$ ) of the outcome variable will be included as covariate to diminish residual variance and to account for inter-individual variance at baseline. Furthermore, sociodemographic variables (age, sex and living situation (alone vs. not alone)) are planned to be included as covariates, too. These variables can be supposed to contribute proportions of variance to the outcome variables which should be independent of possible study effects as the intervention cannot change age, sex or living situation. Thus, the inclusion of these variables should result in decreased residual variance enhancing thereby

the statistical power to detect differences between study groups. A positive intervention effect is then defined as a significant regression coefficient (one-sided test) of the study group variable. The p-values will be interpreted one-sided as one-sided hypotheses are tested. The design of the DelpHi trial allows for multiple testing (five primary outcomes), therefore, additionally the Bonferroni corrected p-values will be reported.

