### **2.3.2.3 Primary Efficacy Analyses (ITT)**

The ITT analyses will be performed following the schedule of the per protocol analyses with the only difference being that missing follow-up values will be imputed.

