#### **2.5 Post Hoc Power Calculations**

The actual power of the trial was assessed during the baseline sampling when first estimates of the ICCs where known, for reasons explained above. Table 1 gives the estimates for the ICC of the baseline values of the primary efficacy endpoints and the detectable intervention effect (power 80%) given an assumed coefficient of variation of cluster sizes of 1, a baseline follow-up correlation of 0.6,

a mean cluster size of 5 and 100 clusters (GP) included into analysis (total n=500). The power analyses were done with STATA 13/SE using the package *clustersampsi*. Note that the estimates reported in table 1 were derived while the baseline sampling was still ongoing.

**Table 1:** Detectable Difference (power 80%) between Intervention (n=250) and Control group (250)

	Intra-Class Correlation	Detectable Difference	Model
Quality of Life	0.061	0.26	linear
Neuropsychiatric Symptoms	0.361	0.43	linear
Caregiver Burden	0.192	0.35	linear

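### The five primary outcomes are corrected by single-step Bonferroni; Holm's step-down version gives the same family-wise guarantee, never rejects less, and recovers power whenever more than one effect is real

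*SAP*

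**What the plan says.** SAP 2.1 lists four primary dimensions, the last with two measurements: "thus, in total five outcome variables are derived". SAP 2.3.1.2 fits a separate mixed model to each outcome and sets the success rule per outcome: "A positive intervention effect is then defined as a significant regression coefficient (one-sided test) of the study group variable". On multiplicity it notes that five primary outcomes are tested and that "additionally the Bonferroni corrected p-values will be reported". SAP 2.3.2.3 adds: "The ITT analyses will be performed following the schedule of the per protocol analyses", with imputation of missing follow-up values as the only difference.

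The SAP names no step-down procedure, significance level or family-wise error target, and attaches no decision to the corrected values. The confidence intervals it specifies in 2.3.1.3 are bootstrap intervals meant to relax distributional assumptions; they are not adjusted for multiplicity.

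**The concern.** Once five separate p-values are to be corrected for family-wise error, plain Bonferroni is dominated. Holm starts at the same threshold, α/5, and relaxes it after each rejection, with no assumption about how the outcomes correlate. The usual reason to keep the single-step form is to have simple matching simultaneous intervals, and the plan asks for none.

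The loss grows with the number of real effects. The plan sets a directional benefit hypothesis on every primary outcome, so several effects at once is the result it hopes for, and that is where Bonferroni gives away most. Outcomes ranked second or later could be shown as failing correction although the same error guarantee would have supported them. The plan also cares about power: 2.3.1.2 adds covariates to gain it, and section 1 says that the design-paper calculation ignored clustering.

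**Working it through.** The SAP gives no corrected power or adjusted level, so there is no figure of the plan to reproduce. The check compares the two procedures directly.

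**Inputs**
- Family of five tests (SAP 2.1, 2.3.1.2), one-sided (SAP 2.3.1.2).
- Level: not stated. Assumed one-sided family-wise 0.05, with 0.025 as the alternative.
- Effect size: assumed equal across affected outcomes. The non-centrality is either 1.645 + 0.842 = 2.49 (80% power at one-sided 5%) or 1.960 + 0.842 = 2.80 (80% power at two-sided 5%). The 80% matches the power used in SAP 2.5.
- Correlation between the five test statistics: not stated. Assumed common, from 0 to 0.6.

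**1. Rules.** Bonferroni rejects when p ≤ 0.05/5 = 0.01. Holm compares the ordered p-values with 0.05/5, 0.05/4, 0.05/3, 0.05/2 and 0.05, stopping at the first failure. Every Holm threshold is at least 0.01, so Holm rejects whatever Bonferroni rejects.

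**2. Illustration with invented p-values** 0.004, 0.011, 0.015, 0.020, 0.30:
- Bonferroni-adjusted: 0.020, 0.055, 0.075, 0.100, 1.0. One rejection at 0.05.
- Holm-adjusted: 5×0.004 = 0.020; 4×0.011 = 0.044; 3×0.015 = 0.045; 2×0.020 = 0.040, raised to 0.045 for monotonicity; 0.30. Four rejections.

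**3. Bonferroni power per true effect.** This is Φ(non-centrality − 2.326). For 2.49 it is Φ(0.16) = 56%; for 2.80 it is Φ(0.475) = 68%. It does not depend on the other outcomes.

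**4. Holm power by simulation** (400,000 simulated trials per setting). Average power per true effect at one-sided family-wise 5%, non-centrality 2.80:

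| True effects | Bonferroni | Holm, corr. 0 | Holm, corr. 0.3 | Holm, corr. 0.6 |
|---|---|---|---|---|
| 1 | 68% | 68.4% | 68.4% | 68.3% |
| 2 | 68% | 70.5% | 70.3% | 70.0% |
| 3 | 68% | 73.0% | 72.6% | 72.0% |
| 5 | 68% | 81.5% | 79.8% | 78.2% |

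With four true effects Holm reaches 75-76% (correlation 0 to 0.5). For non-centrality 2.49, Bonferroni's 56% becomes 58%, 60-61%, 63-64% and 67-69% with two, three, four and five true effects. At one-sided 0.025 with non-centrality 2.80 and independent outcomes, 59% becomes 61%, 63% and 70% with two, three and five.

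**5. Chance of showing every true effect** (non-centrality 2.80, family-wise 5%). With three effects: 32% to 42% at correlation 0, and 40% to 49% at 0.3. With five effects: 15% to 48% at correlation 0, and 27% to 57% at 0.3. The chance of at least one rejection is identical under both methods (for example 96.9% with three independent effects).

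**6. Sample-size equivalent** (correlation 0.3). At a one-sided 1% test, powers of 0.683, 0.726 and 0.798 correspond to non-centralities 2.80, 2.93 and 3.16. Squared ratios to 2.80 are about 1.09 and 1.27. The gain is thus worth about 9% more patients with three true effects and 27% more with five.

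**7. Error control.** With all five nulls true and independent, Bonferroni's family-wise error is 1 − 0.99⁵ = 0.049, and the two methods are identical in simulation. Holm's error stayed at or below 4.9% in every setting (2.46% at the 2.5% level). With three true effects and independence, Bonferroni uses 2.0% of the 5% allowed and Holm 3.8%. In no simulated trial did Bonferroni reject something that Holm did not.

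**The case against.** The best case against is that nothing here is wrong. Bonferroni is valid, the plan calls the trial exploratory, and its success rule rests on the unadjusted one-sided p-value. The corrected values are reported in addition, with no decision attached, so changing them alters no declared conclusion, and a reader can compute Holm values from the five raw p-values. The largest gains need all five outcomes to be affected with equal power, whereas Table 1 shows unequal detectable differences (0.26, 0.43, 0.35) and has no row for the two binary outcomes. Finally, section 1 dates the follow-up analysis to April to October 2016; a switch after results are known, to a method that can only add rejections, would not be neutral.

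Much of this stands. It is an efficiency point and touches only the corrected results. The five-effect figures are an upper case, and with two or three effects the gain in average power is about 2 to 5 points. The unstated level, and the silence on which p-value decides, are weightier gaps, but separate ones.

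The objection does not rescue the choice of method. The corrected values are the only multiplicity-controlled evidence the plan provides. Having chosen to report a correction, it gains nothing from the weaker form. That a reader could compute Holm later is a reason to name it in advance. The timing argument concerns how a change is labelled and does not affect which method is better.

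**Conclusion.** The point holds as a recommended improvement. Holm dominates plain Bonferroni for these five tests, whatever the level or the correlation between outcomes. The size of the gain depends on how many outcomes are truly affected: practically nil for one, about 2 points of average power for two, 4 to 5 for three, and 9 to 13 for all five. These figures assume equal true effects, a common correlation of 0 to 0.6, and a one-sided family-wise level of 5% or 2.5%, none of which the SAP states. The direction of the result needs none of these assumptions.

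**What to change.** In SAP 2.3.1.2, replace the clause on Bonferroni with: *Holm (step-down Bonferroni) adjusted one-sided p-values over the five primary outcomes will be reported.* In 2.3.2.3, state that the same adjustment applies to the ITT analyses.

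The change costs one sentence in each section and needs no extra data, model or assumption. The one drawback is that simultaneous confidence intervals matching Holm are less simple than Bonferroni intervals, and the plan specifies none. If the change is made after follow-up results are known, label it as such and show the Bonferroni values beside the Holm values.

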### **2.3.1.3 Sensitivity Analyses**

Including the GP as random effect variable in the equation using random intercepts only implies that the effect of the GP on the outcome variable is independent of the effects of the predictors which may not be correct for the study group variable and the baseline variable of the outcome. Thus, to test the robustness of the potential treatment effect, in sensitivity analyses random slopes for the baseline variable of the outcome will be introduced into the models. Descriptively, these models allow for GP dependent treatment effect and thus will result in treatment estimates respecting the possibility of differentially collaborating GPs, thus assessing the robustness of the results regardless of a potentially present performance bias.

The treatment effect estimates from the different models will be compared descriptively against each other and, moreover, the random slopes models will be tested against the random intercept models via likelihood ratio tests. Note that these likelihood ratio tests are known to be overly conservative.

Furthermore, in the case of the metric outcomes, we will derive additionally confidence intervals and p-values via non-parametric bootstrapping using 2000 replications. These sensitivity analyses are planned to get confidence intervals and p-values independent on the parametric assumptions of Gaussian distributions and homoscedasticity. Especially in the case of neuropsychiatric symptoms, baseline analyses indicated a skewed distribution for the NPI scores.

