#### **2.4.3 Performance Bias**

As the DelpHi-Trial is conducted in the setting of primary care, the control of the treatment in the control group as “care as usual” is not possible. It could be that already the inclusion of a GP into the study will change the treatment of the included patient. This effect could easily mask potential intervention effects. Thus, a non-significant result cannot be easily interpreted. The treatment adherence of the GPs in the intervention group was evaluated and generally quite high. Nevertheless, it is very plausible that the GPs were different in their adherence to the study protocol. For this reason, we performed special sensitivity analyses (see section “per protocol analyses”). These sensitivity analyses deliver a weak test of the robustness of the effects despite the heterogeneity between the GPs.

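### The sensitivity model said to allow GP-specific treatment effects only lets the baseline slope vary by GP, so agreement with the primary model says almost nothing about additive differences in GP adherence

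*SAP*

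**What the plan says.** SAP 2.3.1.3 starts from a sound worry. A GP random intercept alone assumes that the GP's influence does not depend on the predictors, and this "may not be correct for the study group variable and the baseline variable of the outcome". Two variables are named. The remedy covers one of them: "random slopes for the baseline variable of the outcome will be introduced into the models". The section then states that "these models allow for GP dependent treatment effect and thus will result in treatment estimates respecting the possibility of differentially collaborating GPs". The purpose it draws from this property is given as "thus assessing the robustness of the results regardless of a potentially present performance bias".

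Two readings of the models are planned: "The treatment effect estimates from the different models will be compared descriptively against each other", and the random-slope model is tested against the random-intercept model by a likelihood ratio test (LRT), with a caution that this test is conservative. A bootstrap is added for the metric outcomes, to obtain intervals and p-values "independent on the parametric assumptions of Gaussian distributions and homoscedasticity".

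SAP 2.4.3 uses these analyses as its answer to one form of performance bias. It says that "it is very plausible that the GPs were different in their adherence to the study protocol", gives that as the reason for the analyses, and adds: "These sensitivity analyses deliver a weak test of the robustness of the effects despite the heterogeneity between the GPs".

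**The concern.** A GP-dependent treatment effect needs a term that lets the study-group effect differ between GPs. The planned term lets the relation between baseline and follow-up differ between GPs, in both study groups alike. If some intervention GPs simply achieve more than others by a roughly constant amount, nothing in the added term represents it.

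No other planned analysis fills the gap. The bootstrap protects intervals and p-values against distributional assumptions but does not estimate or test differences between GPs. The predictive mean matching in 2.3.2.4 concerns the imputation method, and the same section drops random slopes for the ITT analyses.

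At stake is an interpretation. A stable estimate and a non-significant LRT are to be expected whether or not GPs differ additively, yet the text presents the exercise as evidence of robustness to differing collaboration.

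**Working it through.** **Step 1: the models side by side.** For patient i of GP j, let G be study group, x the baseline outcome, u GP random effects and e the residual.

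- Primary (2.3.1.2): y_ij = a + b·G_j + c·x_ij + covariates + u0_j + e_ij
- Sensitivity (2.3.1.3): the same plus u1_j·x_ij
- A GP-dependent treatment effect would be the primary model plus t_j·G_j

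The treatment effect is the single coefficient b in both planned models. GPs are the randomised units, so G_j is constant within a GP and t_j·G_j is a GP-level constant. It merges with u0_j. If t_j has SD τ and is independent of u0_j, the GP variance is σ² in the control group and σ² + τ² in the intervention group. Additive heterogeneity therefore appears as unequal GP variances, which neither planned model allows.

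**Step 2: variance components from SAP 2.5, Table 1.** The SAP gives no figure for this claim, so there is none to reproduce. Table 1 assumes 100 GPs, mean size 5, cluster-size CV 1 and baseline–follow-up correlation 0.6, so the variance left after baseline is 1 − 0.6² = 0.64. Then GP SD = √(ICC × 0.64) and residual SD = √((1 − ICC) × 0.64).

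| Endpoint | ICC | GP SD | Residual SD | Intervention GP SD if τ = 0.3 | Ratio |
|---|---|---|---|---|---|
| Quality of life | 0.061 | 0.198 | 0.775 | √(0.0390 + 0.09) = 0.359 | 1.82 |
| Caregiver burden | 0.192 | 0.351 | 0.719 | √(0.1229 + 0.09) = 0.461 | 1.32 |
| NPI | 0.361 | 0.481 | 0.639 | √(0.2310 + 0.09) = 0.567 | 1.18 |

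The last column shows why unequal variances are hardest to see for the NPI.

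**Step 3: simulation.** Assumptions not in the SAP: 50 + 50 GPs, Gaussian outcomes, mean effect 0.3 SD, the values of τ, GP effects independent of GP intercepts, and the Table 1 baseline ICCs holding for follow-up given baseline. Fits are by maximum likelihood. The planned LRT (intercept plus correlated baseline slope) is referred to chi-square with 2 df. The LRT for a GP variance free in each study group uses 1 df. There are 1,000 trials per setting (600 for quality of life with 25% loss), with Monte Carlo SE at most 1.7 percentage points. Entries are rejection percentages for quality of life / burden / NPI.

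| Truth | Planned LRT | Free-variance LRT |
|---|---|---|
| No heterogeneity | 2.0 / 1.8 / 3.0 | 4.6 / 6.1 / 5.5 |
| Additive, τ = 0.3 | 2.5 / 2.8 / 2.5 | 35 / 18 / 10 |
| Additive, τ = 0.5 | 2.5 / 2.7 / 1.9 | 83 / 62 / 48 |
| Additive, τ = 0.6 | 2.0 / 3.2 / 2.4 | – |
| Effect scales with baseline, slope SD 0.3 | 58 / 63 / 73 | – |
| τ = 0.3, 25% of patients lost | – | 22.5 / 15.2 / 10.5 |
| τ = 0.5, 25% of patients lost | – | 77.2 / 55.6 / 40.5 |
| Intervention halves the GP SD | – | 8 / 41 / 71 |

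The mean absolute difference between the random-intercept and random-slope estimates was 0.008–0.010 SD with additive heterogeneity and 0.007–0.009 without. The descriptive comparison is as uninformative as the test.

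**Step 4: does this depend on the set-up?**

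- Independent instead of correlated intercept and slope (200 trials, quality of life / NPI): planned LRT 1.5 / 2.0% with no heterogeneity and 3.0 / 3.0% at τ = 0.5.
- Lognormal or exponential cluster sizes (600 trials each): planned LRT 1.3–2.5%; free-variance LRT 35–37 / 14–15% at τ = 0.3 and 86–87 / 48–51% at τ = 0.5 (quality of life / NPI).
- A cruder run with GP variance 0.1, residual SD 0.75 and 60 trials per setting, with τ up to 1.0: at τ = 1.0 the two estimates were 0.295 and 0.294. The heterogeneity went into the intercept variance (0.09, 0.23 and 0.62 at τ = 0, 0.5 and 1.0), while the estimated slope variance stayed near 0.005. The planned LRT rejected in 0, 5 and 7% of trials, rough figures at that size.

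**The case against.** The strongest reply is that the plan asks whether the estimate is robust, and against additive differences it is. The GP intercept absorbs them: with equal GP numbers the primary model had bias of at most 0.006 and coverage of 93–95.5%, and in a run of 250 trials the quality-of-life standard error rose from 0.084 to 0.114 at τ = 0.5, as it should. This stands, and no bias in the primary estimate is alleged. But that reassurance comes from the primary model. The random-slope model adds nothing to it.

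Secondly, the planned LRT does detect GP effects that scale with baseline. This also stands, so the conclusion is confined to additive differences.

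Thirdly, the plan hedges. It calls the check weak and the LRT conservative, reports that GP adherence was assessed and mostly high, attaches no decision rule, and nowhere says that a non-significant LRT proves robustness. These points limit the harm. They do not correct the description: the hedges suggest low power, whereas this kind of heterogeneity is not modelled at all.

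Lastly, the free-variance model is itself limited. Its power is low at τ = 0.3, it cannot attribute unequal variances to adherence, it covers three of five endpoints, and it rejected in only 1–4% of trials (250 per setting) when effects scaled with baseline. All true. It complements the planned model rather than replacing it, and adding it is optional.

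**Conclusion.** The concern holds. The contradiction lies within 2.3.1.3 and follows from the model specification alone: two variables are named as problems, a slope is added for one, and the model is credited with handling the other. Section 2.4.3 then relies on that credit.

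The size of the effect on interpretation depends on assumed heterogeneity, since the SAP gives none. For additive SDs of 0.3 to 0.6 the planned LRT rejects in 1.9–3.2% of trials, against 1.8–3.0% with no heterogeneity, and the estimate shifts by about 0.01 SD either way. Agreement between the two models is therefore no evidence that the results withstand GPs who differ additively in what they achieve.

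The two binary endpoints were not simulated; the algebraic point applies to their linear predictors too. The text should be corrected, but neither the primary estimate nor any planned decision is called into question.

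**What to change.** 1. In 2.3.1.3, describe the random-slope model as a check of whether the baseline relation varies between GPs. Delete the statement about GP-dependent treatment effects and the statement that robustness is assessed whatever the performance bias.
2. For the three metric endpoints, add a model with the GP intercept variance estimated freely in each study group, so that the intervention variance may be larger or smaller than the control variance. Report the treatment estimate with its confidence interval, both GP variances, and the LRT against the common-variance model (chi-square, 1 df).
3. In 2.4.3, refer to that model and state its limits: it cannot separate adherence from other causes of unequal GP variance; power is low for modest heterogeneity and for high-ICC endpoints such as the NPI; a non-significant result does not show uniform adherence.

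If the extra model is not wanted, step 1 is still needed, and 2.4.3 should say that differing GP adherence is not tested.

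The cost is wording in two sections and one more mixed model for each of three endpoints, with no new data. The drawback is that a GP variance may be estimated at zero in one study group, most likely for quality of life, which has the lowest ICC.
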